## Subjects may be withdrawn for any of the following reasons:

- If clinically significant and/or personally intolerable moderate or severe adverse events occur that cannot be addressed by dose adjustment or addition of concomitant medications (these can be discussed with SC and Medical Monitor. Investigators are encouraged to try dose reduction or addition of concomitant medications prior to withdrawal of participants).
- If a subject is worsening clinically (they have 6 much worse or 7 very much worse on CGI-I), there has to be a return visit/phone call within 1-2 weeks to revisit/re-evaluate with CGI-I. If the subject still has 6 or 7, then case must be discussed with SC and Medical Monitor to get approval for participation to continue.
- Study noncompliance
- Study physician discretion

#### Subjects **must be withdrawn** for the following reasons:

- At the participant or guardian request
- If the medical monitor feels worsening of their clinical condition or life threatening adverse events are likely to be related to the study treatment or procedures.

#### 8.6 Safety Oversight

#### **8.6.1 Independent Medical Monitor**

has a wealth of experience in pediatric oxytocin administration as she has conducted many of her own trials. She will serve as the independent medical monitor for this study. She will review alarm values of labs and ECGs as defined by site treating physician and/or site PI, UPs, SAEs, pregnancies, serious suicidal ideation. and serious adverse events within 14 working days of their reporting. She will also review all new treatment emergent adverse effects of moderate or greater severity two times a year prior to DSMB meetings. She will be available to DSMB and to steering committee to discuss concerns about safety related to the 2 above activities. She will also discuss any case in which an individual participant has significant worsening reflected by a CGI-I of 6 or 7 that has not improved over the course of 8 weeks and/or with dose reduction.

### **8.6.2** Data Safety Monitoring Board (DSMB)

The UNC TRACS Data and Safety Monitoring Board (DSMB) will monitor data from all sites. The principle role of the DSMB is to monitor the data from clinical trials to protect the safety of the research participants. To achieve this, the DSMB will: a) establish a 2 times/year schedule; b) review proposed protocols for safety and validity; c) evaluate recruitment and rate of enrollment in relation to the projected activity; d) monitor the occurrence of adverse events, serious adverse

events, and early withdrawals or terminations throughout the course of the study; e) review with a designated research staff member the pattern of the study data; and f) evaluate study outcomes, when available. It will be reviewed by the DSMB 2 times/year.

## 8.6.3 Overall Study Stopping Criteria

At 26 week intervals, the study biostatistician will test whether there are significant differences between those on active treatment and those on placebo for Severe and Life Threatening/Fatal adverse events. The statistical analysis method will be a Fisher Exact Test. The significance level considered significant for these tests will be 0.05 without correction for multiple comparisons. If there are any significant differences that indicate greater risk for active treatment, further enrollment will be stopped, but participants currently being treated will continue. These results will be provided to the DSMB along with the summary report of enrollment and other safety data at their next regularly scheduled meeting. If the DSMB will evaluate the apparently increased risk and work with the SOARS Steering committee as necessary to develop a mutually acceptable plan for addressing the apparently increased risk. Such decisions might involve closing the study entirely, changing dosing or implementing additional monitoring.

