#### PROTOCOL SUMMARY

Study of Oxytocin in Autism to improve Reciprocal Social

Title: Behaviors

**Synopsis:** This Phase 2 study will evaluate oxytocin as a supplemental

treatment for improving social difficulties in individuals with

autism.

**Objectives:** We will randomly assign 300 individuals between the ages of 3 -

17 years old with an autism spectrum disorder to 24 weeks of treatment with oxytocin or a matched placebo across six sites in the United States. Subsequently all participants will receive open-label oxytocin for 24 additional weeks. Post-treatment assessments will be done ~4 weeks after treatment stops. We will also determine *OXTR* methylation status at baseline, 8 weeks, 24 weeks and 36 weeks to explore potential relationships between *OXTR* methylation and baseline severity of social

problems and/or treatment response.

**Population:** 300 subjects, male or female, ages 3-17 with an autism spectrum

disorder

Phase: 2

**Number of Sites:** 6 treatment sites

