## **Suggested Titration to the Target Dose**

Blinded Phase: In the double-blind phase, titration to the target dose is expected to take 8 weeks and follow the suggested table below unless there are issues with tolerance or compliance. Dosing will begin at 8/0 IU in the AM at baseline. Typically, the dose will increase to 8/0 IU twice daily (BID) (16/0 IU TDD) at week 2. Dose will then be increased by 8/0 IU twice daily (BID) at weeks 4 and 8 with TDDs of 32/0 IU and 48/0 IU respectively. During the initial titration period (baseline to week 8), dosing increases should never occur before the time point specified in the schedule. Specifically one could not go to a TDD of 16/0 IU prior to week 2, or 32/0 IU prior to week 4 or 48/0 IU prior to week 8.

Week 0	Week 2	Week 4	Week 8
8 IU qD	8 IU BID	16 IU BID	24 IU BID
(8 IU TDD)	(16 IU TDD)	(32 IU TDD)	(48 IU TDD)

**Open Label Phase:** In the open-label phase, from week 24 to week 28, the dose will be 24IU in AM for a TDD of 24 IU. From week 28-36 the dose will be 48 IU TDD (ie. 24 IU BID). At week 36 the dose can be increased to 72 IU TDD (ie. 48 IU in the morning and 24 IU in the afternoon).

Week 24	Week 28
24 IU qAM	24 IU BID
(24 IU TDD)	(48 IU TDD)

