SOARS-B Parent Dose Sheet 		İχ	X	X	Х		Х	X	Х	X	X	X	
Risks Handout		İΧ				1			Х				
Medication Compliance 				Х	X	1	X	X	Х	X	X	X	X
Oxytocin Dosing Log (staff)	i	İx	İх	X	X		X	X	X	ΪX	X	l x	l x
Medication Diary Dispensed	1	X		X	X		X	X	X	X	X	X	

0-CGI-S only at baseline, CGI-I and CGI-S at most other time points (office visits)

- 1-Required at screening but can be done at any time during the course of the study at physician discretion. Must have a negative pregnancy test within two weeks of baseline
- 2-Safety labs to include: glucose (random), CO2, Cl, K, Na, Creatinine, BUN, AST, ALT, full urinalysis, urine pregnancy in pubertal girls Screening safety labs must be repeated if more than 12 months between screening and baseline
- 3- Assessment will be obtained only in participants who have fluent phrase speech & can define basic feelings and friendship
- 4- Completed each time the participant returns study medication
- 5- The appropriate SOARS-B Parent Dose Sheet should be given at each time dose changes to parents
  - 6-Stanford Binet or Mullen may be completed at physician discretion
  - 7- At physician discretion

  - \*Must be given at baseline, but also can be given at any other time during the course of the study at study staff discretion
    \*\*Optional redraw of mRNA, plasma/salivary oxytocin, and methylation at baseline for those who may have had a lengthy time between screening and baseline (not safety

Procedures for visits are allowed to be completed on separate days, however, subjects may not be dispensed open label medication until all week 24 procedures are completed

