### 8.3.2 Duke Reporting to Other Regulatory Bodies

Medical Monitor: Duke will report all SAEs, UPs and other reportable events (section 8.2) to the medical monitor within 14 days and receive acknowledgment that she has reviewed them.

DSMB: Duke will report SAEs, UPs and other reportable events (section 8.2) that are considered possibly related to study treatment to the DSMB within 14 days of being made aware of their occurrence.

FDA: To be reportable to the FDA, the event must meet 3 criteria. The investigator or the holder of the IND may make the determination if the event meets all three of the following criteria.

- Suspected Adverse Reaction: meaning there is a reasonable probability that the drug caused the event. Meaning there is evidence to suggest a causal relationship between the drug and the adverse event.
- Serious (use definition of serious in section 8.2.1)
- Unexpected (use definition of unanticipated in section 8.2.2)

Timelines for reporting to the FDA:

- Unanticipated fatal or life threatening adverse events (7 days)
- Unanticipated non-fatal/non-life threatening (14 days)

Steering Committee: Duke will report all SAEs/UPs/other reportable events (section 8.2) to the steering committee within 14 business days of Duke's awareness.

Duke's local IRB: The coordinating center is responsible for reporting unanticipated problems to their local IRB as their local IRB has direct oversight of Duke and indirect oversight of other sites.

The timelines for reporting unanticipated problems to the IRB are:

- Unanticipated Problems that are serious adverse events should be reported to the IRB within one (1) week of the investigator becoming aware of the event.
- Any other Unanticipated Problem should be reported to the IRB within two (2) weeks of the investigator becoming aware of the problem.
- Other reportable events (section 8.2): during annual renewal

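### A positive between-arm safety test has no deadline for reaching the DSMB, and nothing written pauses the week-24 start of open-label oxytocin while it waits

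*Combined protocol and SAP*

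**What the plan says.** Protocol v6.0, section 8.6.3 (Overall Study Stopping Criteria), has the study biostatistician compare active and placebo every 26 weeks on severe and on life-threatening/fatal adverse events. The test is Fisher's exact at 0.05, with no multiplicity correction. If it shows greater risk on active treatment, "further enrollment will be stopped, but participants currently being treated will continue". The results go to the DSMB "along with the summary report of enrollment and other safety data at their next regularly scheduled meeting". The DSMB then works out a plan with the Steering Committee, which may mean closing the study, changing dosing or adding monitoring.

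On meeting frequency, section 8.6.2 says "It will be reviewed by the DSMB 2 times/year". Section 5.6 of the final SAP gives the same frequency.

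Section 8.3.2 sets a separate clock for individual events. The lead site must report SAEs, unanticipated problems (UPs) and other reportable events "considered possibly related to study treatment to the DSMB within 14 days of being made aware of their occurrence".

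On what happens at week 24, the Protocol Summary says "Subsequently all participants will receive open-label oxytocin for 24 additional weeks". The titration section adds that "from week 24 to week 28, the dose will be 24IU in AM for a TDD of 24 IU". The footnotes to the Schedule of Events state one condition for the switch: "subjects may not be dispensed open label medication until all week 24 procedures are completed".

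**The concern.** Once the rule has fired, children can be newly exposed to the flagged product by two routes: enrolment, and the placebo arm's switch at week 24. Section 8.6.3 closes the first at once. It is silent on the second, and it sends the group-level result by the routine reporting cycle. One possibly related SAE thus has a 14-day clock to the DSMB, while a statistically significant excess of severe or fatal events across the arms has none.

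At stake is whether some placebo children start open-label oxytocin before the DSMB has seen a signal that the protocol itself regards as strong enough to stop enrolment. Section 1.3 of the protocol describes information on the safety of sustained use as limited.

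**Working it through.** The plan states no figure to reproduce, so the check is a reading of the text followed by an illustration of size.

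**Reading the text**

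- *Deadline for the test result.* Sections 8.6.3 and 8.6.2 and SAP 5.6 contain no number of days, no ad hoc meeting, and no link between test dates and meeting dates.
- *Pause of the switch.* The Protocol Summary, the titration section, the week-24 visit description and the Schedule of Events contain no condition tied to a positive test. That placebo children go on to oxytocin in the interval follows from reading these places together; 8.6.3 does not mention the switch.
- *Other routes.* The SAE and UP reports (8.3.1, 8.3.2), the medical monitor's review (8.6.1) and the individual withdrawal rules (8.5) work case by case. None is written to carry the between-arm result. Severe events that are neither serious nor unexpected are seen by the medical monitor twice a year (8.6.1).

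**Illustration of size**

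Inputs from the documents: final sample size 290 (protocol 10.2; SAP section 6), 1:1 allocation (SAP 1.3), so 290/2 = 145 on placebo; blinded phase 24 weeks.

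Assumed: uniform accrual over 78 to 104 weeks and no dropout. The documents do not give accrual length. Randomisation began in December 2014 and the target was revised on 28 March 2016. If enrolment was still open then, accrual lasted at least 453 days from 31 December 2014, or 64.7 weeks.

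Placebo children reaching week 24 per week = 145 / accrual weeks:

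- 78 weeks: 145/78 = 1.86
- 104 weeks: 145/104 = 1.39

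Switches during a delay of D weeks (D up to 24) = rate × D; share of blinded placebo children = D/24:

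| Delay D | 78 weeks' accrual | 104 weeks' accrual | Share |
|---|---|---|---|
| 2 weeks | 3.7 | 2.8 | 8% |
| 4 weeks | 7.4 | 5.6 | 17% |

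Cutting an assumed 4-week gap to 2 weeks spares 3.7 or 2.8 early switches each time the rule fires. Longer accrual lowers the rate: 145/156 = 0.93 per week at 156 weeks.

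**How often the rule would fire**

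The protocol gives no severe-event rate. A simulation assumed 145 per arm, uniform accrual, exponential time to first event, and placebo risks of 5/10/20% over 24 weeks. It compared randomised arms on blinded-phase events by two-sided Fisher p < 0.05 with the excess on active. Looks were every 26 weeks, counted only while enrolment was open, with 6,000 trials per setting and Monte Carlo error of at most 0.7 points.

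| Hazard ratio | 78 weeks' accrual (5/10/20% risk) | 104 weeks' accrual (5/10/20% risk) |
|---|---|---|
| 1 | 1.6 / 2.4 / 3.2% | 2.1 / 3.6 / 5.0% |
| 2 | 15.5 / 31.4 / 55.9% | 21.8 / 42.1 / 69.7% |

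At hazard ratio 2 and 10% risk, expected early switches per trial are 0.314 × 7.4 = 2.3 (78 weeks) with a 4-week gap, and 0.314 × 3.7 = 1.2 with a 2-week gap. The 104-week case gives about the same. The difference is about one child per trial.

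**The case against.** **The delay may be short.** Tests are 26 weeks apart, the DSMB meets twice a year, and the result travels with the routine report. The natural reading is that the test is run for that report. A reader might go the other way: two evenly spaced meetings are 52/2 = 26 weeks apart, longer than the blinded phase, so every blinded placebo child (about 33 to 45) might switch before the DSMB hears. The documents do not support that as an expected delay. They do not document any gap; they only fail to bound one. The 4-week figure above is likewise assumed.

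**The UP route may already cover it.** Section 8.2.2 defines a UP to include an outcome unexpected in frequency that suggests greater risk. A between-arm excess could be argued to qualify, and would then carry the 14-day clock of 8.3.2. This is arguable but not stated, and the specific timing in 8.6.3 governs on its face.

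**Others can act.** A reader might infer that only the DSMB can stop the switch. The documents do not say that. Treating physicians may interrupt study drug (5.5), the medical monitor can require withdrawal of an individual (8.5), and the plan under 8.6.3 is agreed with the Steering Committee. Nor can the absence of an ad hoc meeting rule in the DSMB's own charter be inferred, since no charter is included.

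**The effect is small.** Child-weeks on oxytocin before review are rate × D²/2: about 15 or 11 at 4 weeks, and 3.7 or 2.8 at 2 weeks, a difference of about 11 or 8. At 10% risk and hazard ratio 2 the excess hazard is −ln(0.9)/24 = 0.0044 per week. That is 0.04 to 0.05 severe events per firing, or about 0.015 per trial after weighting by the 31 to 42% chance of firing. This stands, on its assumptions.

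**The limited action looks deliberate.** The change log says stopping language was added at the DSMB's request. That is a reason to leave the automatic action alone, and the change proposed here does so.

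**Conclusion.** The point holds as a gap in wording. Section 8.6.3 routes a positive between-arm test to the DSMB's next regular meeting with no deadline or out-of-cycle review, although possibly related individual SAEs and UPs have 14 days. Nothing written pauses the week-24 switch in the interval.

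The text does not show that the delay is long in practice or that children would be harmed by it. The size depends on assumed accrual, gap and event risks. On those assumptions it is about 1.4 to 1.9 switches per week of delay once the rule has fired, and about one fewer early switch per trial from shortening 4 weeks to 2. If results already reach the DSMB within 14 days, the change gains little beyond making that a requirement. Because it costs so little and concerns children's safety, it is worth making, at low to moderate priority.

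**What to change.** In 8.6.3, replace delivery at the next regular meeting with words to this effect: a positive test is notified to the DSMB as soon as it is found, and within 14 days at most, for out-of-cycle review; that review expressly considers whether children due at week 24 should start open-label oxytocin; any hold applies to both arms, so that allocation is not revealed.

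The 14 days is the protocol's own limit from 8.3.2. The automatic stop of enrolment and the continuation of treated children stay as they are.

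The cost is a protocol wording change and an occasional extra DSMB call, in about 1 to 5% of trials with no drug effect under the assumed 5 to 20% risks. A hold would also delay or interrupt treatment for children in the oxytocin arm, so it should be a considered decision at that review and not automatic.

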#### 8.6.4 Cardiac Monitoring Plan

Based on the patient's age, gender, and height percentile, we have adapted blood pressure parameters where blood pressures above or below the set threshold will prompt the PI to consider doing an EKG. These parameters were derived from the National High Blood Pressure Education Program Working Group on High Blood Pressure in Children and Adolescents(Falkner, Daniels et al. 2004). We have likewise adapted parameters from Pediatric cardiology for practitioners(Park 2008) and Normal ECG standards for infants and children (Davignon, Rautaharju et al. 1979)to establish heart rate guidelines where patients whose heart rate is above or below these thresholds will be considered for an EKG at every visit. Finally, we will incorporate clinical signs and symptoms of cardiac risk into our assessment with the vital sign measurement and specifically query for the presence of syncope, dizziness, palpitations, shortness of breath, and bradycardia or tachycardia. The clinical parameters will be incorporated into the SLAES. The specific parameters for heart rate, blood pressure are located in Appendix A. We believe, given the low cardiac risk of oxytocin, that careful monitoring of vital signs and clinical signs and symptoms at every visit will be adequate to ensure the safety of our patients.

#### 9 CLINICAL MONITORING

### 9.1 Site Monitoring Plan

Site monitoring will be conducted to ensure that the human subject protection, study procedures, laboratory, study intervention administration, and data collection processes are of high quality and meet the sponsor, ICH E6 and, when appropriate, regulatory guidelines. This section will give a general description of how site monitoring will be conducted. The data monitor will be housed at the Data Center at UNC Chapel Hill. The Data/Regulatory Monitor will monitor the database, with the data manager, in order to assess quality assurance and control issues, and will generate queries from the database. This individual will also monitor each site's regulatory documents for

completeness and accuracy (delegation of duties logs, 1572s, FDFs, general correspondence, IRB correspondence, laboratory values etc). He/she will travel to each site in order to monitor the study coordinators and the case report forms to ensure that data are collected completely and accurately. Specifics of site monitoring will be included in the separate data monitoring plan. He/she will ensure that queries are resolved. He/she will also ensure that data is properly and accurately entered into the database.

### 10 STATISTICAL CONSIDERATIONS

The overall statistician or his/her designee will conduct and have ultimate responsibility for all data analysis described below. All statistical computing will be done using the most recent version of SAS. The lead statistician will do the programming and perform the analyses. The analyses described below will be performed on the intent-to-treat population. Additional exploratory analyses may be performed on the per protocol population or key subsets of the sample (e.g. those participants without fluent phrase speech). All data will be explored using descriptive statistics and graphical techniques prior to any hypothesis testing. For categorical variables, we will examine frequency distributions and where appropriate contingency tables and histograms. For continuous variables, we will examine frequency distributions and, where appropriate, box-and-whisker plots. When appropriate, we will consider transformation. If necessary due to distributional considerations, we will cautiously consider a change of analysis method to a less parametric one.

# 10.1 Statistical Analysis (Please also see SAP)

General Modeling: Unless otherwise specified, we will fit a mixed longitudinal model with change from baseline to each post-baseline month (4 weeks) for a response variable, functioning (low versus high) as the stratification variable, center as a blocking factor, treatment (oxytocin versus placebo) as the between-subjects factor, week as a within-subjects factor, their interaction, and baseline as a covariate. The primary model used will be a mixed model with repeated measures (MMRM), treating week categorically and using an autoregressive (with a lag of 1) covariance structure. As a secondary sensitivity analysis, we will fit a random coefficients model treating week continuously with random coefficients for the intercept, slope, and slope squared, with an unstructured structure among the random coefficients. The primary hypothesis test of interest will be a test of treatment effect at week 24. Distributional assumptions will be examined using residuals. These mixed models could fail to converge or encounter difficulties based on their use of asymptotics. If they do, we will attempt to simplify the models in order to eliminate the problems, and if necessary, move to analyses that assume compound symmetry, but use a Huynh-Feldt correction if compound symmetry fails.

Missing Data: The mixed models used to evaluate the continuous response variables are able to handle moderate amounts of missing data provided they are missing at random. We will examine the missing at random assumption by assessing baseline differences between dropouts and completers, as well as differences in response variables up to the point of premature withdrawal. If the missing at random assumption does not appear to be tenable, we will report the mixed models results but spend additional effort characterizing treatment effect at time of premature withdrawal or the effect of not including participants with significant missing data in supplementary analyses.

